**Table Shells:**

**Table 1: Study Population Characteristics**

	Hematoma present on CT N=	Hematoma not present on CT N=	Total N=	p-value
Gender Female Male				
Age N Mean (SD) Median Q1, Q2				
Skin Color				
Hair Color				
Hair Thickness				
Hair Length				
Mechanism of Injury Fall from elevation MVC Etc.				
Mortality				
GCS N Mean (SD) Median Q1, Q2				
Blood volume Left frontal Right frontal Etc. (?)				
Loss of Consciousness Yes No				
Location Frontal Temporal Occipital Parietal				
Hematoma Type SDH EDH Etc.				

**Table 2: 2x2 Contingency Table of CT and InfraScanner results**

	Hematoma CT		
Hematoma InfraScanner	No	Yes	Total N=
No			
Yes			
Total N=			

**Table 3: 2x2 Contingency Table of CT and InfraScanner Results for SDH**

	Hematoma CT of SDH		
Hematoma InfraScanner of SDH	No	Yes	Total N=
No			
Yes			
Total N=			

Similarly, for EDH, etc.

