10. Device Description/Mechanism: The following description is adapted from the InfraScanner White Paper (20): All biological tissue is, to differing extent, permeable to electromagnetic radiation of different frequencies and intensities. This can also be considered permeability to photons of different energy levels. This permeability to electromagnetic energy is the basis of all imaging based on transmission/scattering characteristics such x-ray, Computed Tomography, and near-infrared, NIR, imaging. From the principles of spectroscopy, it is also known that different molecules absorb different wavelengths of electromagnetic radiation (which is synonymously referred to as light at shorter wavelengths). Similarly, tissue scatters radiation to different degrees. The Infrascanner is concerned with NIR imaging of the hemoglobin molecules. From any light source, photons follow a characteristic path through the target tissue back to a detector on the same approximate plane as the source. While the light is severely attenuated due to the scattering and absorption process, it is nonetheless encoded with the spectroscopic signatures of the molecules encountered en route to the detector (Image C).

The principle used in identifying intracranial hematomas with the Infrascanner is that extravascular blood absorbs NIR light more than intravascular blood. This is because there is a greater (usually 10-fold) concentration of hemoglobin in an acute hematoma than in normal brain tissue where blood is contained within vessels. The Infrascanner compares left and right side of the brain in four different areas. The absorbance of NIR light is greater (and therefore the reflected light less) on the side of the brain containing a hematoma, than on the uninjured side. With specified wavelength ranges, optical light source(s) or emitter(s) and a photodetector are placed at a distance, which allows proper NIRS absorption measurements in a desired volume of tissue. The wavelength of 805nm is sensitive only to blood volume, not to oxygen saturation in the blood (Image D).

The Infrascanner is placed successively in the left and right frontal (F), temporal (T), parietal (P), and occipital (O) areas of the head and the absorbance of light is recorded. Specifically the placement is as follows:

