Frontal Left/Right forehead, above the frontal sinus; Temporal In the Left/Right temporal fossa; Parietal Above the Left/Right ear, midway between the ear and the midline of the skull; Occipital Behind the Left/Right ear, midway between the ear and the occipital protuberance (Image B).

The difference in optical density (ΔOD) in each of the four symmetrical areas is calculated on a pair-wise basis from the following formula:

$$\Delta OD = \log_{10} \left(\frac{I_N}{I_H} \right) = \log_{10}(I_N) - \log_{10}(I_H)$$

where I_N = the intensity of reflected light on the normal side, I_H = the intensity of reflected light on the hematoma side.

In summary: The Infrascanner includes three components: (1) the Scanner, (2) the Disposable Shield and (3) a Cradle. The Scanner includes a safe NIR diode laser and a silicon detector. The light to and from the laser and detector are optically coupled to the patient's head through the disposable shield optical fibers. The optical fibers are long enough to reach through hair and contact the scalp. The optical fibers are placed 4 cm apart allowing optimal detection of hematomas. The extended fiber optics eliminates the need to shave off any hair. And because the fiber optic piece is disposable it prevents cross contamination. The detected light passes through an optical NIR band-pass filter in order to minimize background light interference. Electronic circuitry is included to control laser power and the detector signal amplifier gain. The detector signal is digitized and analyzed by a single board computer, SBC, in the Scanner. The SBC receives the data from the detector and automatically adjusts the settings of the Scanner to ensure good data quality. The data is further processed by the SBC and the results are displayed on the screen. Readout of the scan provides information on the severity of a hematoma and identifies the region of the brain bleeding. A higher optical density in the scanned region indicates a larger hematoma (20).

- 11. Risk/Benefit Assessment:** There are neither any specific clinical benefits to the research participant, nor are there any direct incentives, financial or otherwise, provided to the research participant. There is no known health risk of interval, short-term use of the device.
- 12. Costs to the Subject:** No additional costs to the patient will be incurred as a result of this add-on, intraoperative research protocol.

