**Variables:**

1. Age: continuous
2. Sex: male/female
3. Skin color: white/light brown/dark brown/black/yellow
4. Hair thickness: bald/thin/medium/thick/MPB
5. Hair color: NA/white/grey/blond/light brown/dark brown/black/red
6. Hair length: bald/0-1 inch/1-3 inches/3-6 inches/>6 inches
7. Scalp hematoma present: Y/N, if yes, Y/N at 8 different locations (left/right frontal/temporal/parietal/occipital)
8. Scalp laceration present: Y/N, if yes, Y/N at 8 different locations (left/right frontal/temporal/parietal/occipital)
9. Scalp fracture present: Y/N, if yes, Y/N at 8 different locations (left/right frontal/temporal/parietal/occipital)

10. Positive infrascan: Y/N
11. Positive CT: Y/N, if yes, Y/N at 8 different locations (left/right frontal/temporal/parietal/occipital)
12. Ventricular effacement: Y/N
13. Midline shift: Y/N
14. CT blood location: Y/N, if yes, Y/N at 8 different locations (left/right frontal/temporal/parietal/occipital)
15. CT blood size: in cubic centimeters (cc) at 8 different locations (left/right frontal/temporal/parietal/occipital)
16. Distance-from-cranium: TBD

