### **Statistical Analysis:**

#### **Definitions of the statistics of interest:**

Let A+ denote the event that the test is positive for hematoma and B+ denote the event that a hematoma is present. Sensitivity,  $P(A+/B+)$ , will be defined for each patient (scan) as the probability that a true hematoma as determined by CT scan will be detected (14). Similarly, let A- denote the event that the test is negative for hematoma and B- denote the event that a hematoma is not present. Specificity,  $P(A-/B-)$ , will be defined as the probability of being negative for hematoma on the InfraScanner 2000™ scan within 30 minutes of CT given the patient has no hematoma present.

The false positive rate will be defined as  $PF+ = P(B-/A+) = P(A+/B-)[1-P(B+)]/P(A+)$ . Similarly, the false negative rate will be defined as  $PF- = P(B+/A-) = [1-P(A+/B+)]P(B+)/[1-P(A+)]$ . Estimates for the false positive and false negative rates will be provided for a range of values for the prevalence of hematomas.

1. Estimation of test characteristics with 90% confidence at the patient level using SAS 9.4;
2. Estimate test characteristics at the scan level (treat each measurement as independent sample) and 95% confidence intervals will be computed as a secondary analysis.
3. Estimating Receiver Operating Characteristic (ROC) curves with patient and scan as the units of analysis with 95% confidence interval.
4. Fit a logistics regression of correct and incorrect detection from InfraScanner, adjusting for age, gender, skin color, hair color, hair thickness, hair length, scalp hematoma, scalp laceration, scalp fracture, ventricular effacement and midline shift.

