#### **Analysis plan:**

1. A baseline table (Table 1) will describe overall study cohort characteristics by hematoma status.
2. Hematoma characteristics will be summarized at the patient level and also at the scan level (Table 2 and Table 3).
3. A 2x2 table of CT and InfraScanner results. Sensitivity, specificity, false positive value, false negative value, and their 95% confidence intervals will be calculated at patient level using the contingency table and reported. Repeat the analysis at scan level.
4. 2x2 tables of CT and InfraScanner results by quadrant. Corresponding counts and test characteristics will be calculated for each quadrant (frontal, temporal, parietal, and occipital). Repeat the analysis at scan level.
5. 2x2 tables of CT and InfraScanner results for hematomas within the detection limit. Corresponding counts and test characteristics will be calculated for hematomas within the detection limit (blood volume > 3.5 cc and distance from cranium < 2.5 cm). Repeat the analysis at scan level.

6. 2x2 tables of CT and InfraScanner results by types of hematoma. Corresponding counts and test characteristics will be calculated for each type of hematoma (SDH, EDH, etc.). Repeat the analysis at scan level.
7. 2x2 tables of CT and InfraScanner results by types of hematoma for those within the detection limit. Corresponding counts and test characteristics will be calculated for each type of hematoma (SDH, EDH, etc.) for those within the detection limit (blood volume > 3.5 cc and distance from cranium < 2.5 cm). Repeat the analysis at scan level.
8. Minimum blood volume detected as positive by InfraScanner 2000 will be reported.
9. Distributions of Blood Volumes and Difference in Optical Density ( $\Delta OD$ ) will be plotted for patients with hematoma.
10. InfraScanner results for special cases will be reported. Special cases include: patients who died, or had surgeries (craniectomy or craniotomy), or had ventricular effacement or midline shift.
11. Logistic regression model will be fit to assess the association between InfraScanner result and potential confounders that include patient age, sex, hair length, hair thickness, hair color, skin color, scalp laceration, scalp fracture, and scalp hematoma. Odds ratios with 95% CI will be reported.

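### SAP Table 3 asks for a device result by bleed type that the documents do not describe, and its CT-negative column, as labelled, takes in patients with another hematoma type

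*SAP*

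**What the plan says.** Table 3 of the SAP's table shells is a 2x2 table for SDH, with the instruction to do the same for EDH and other types. Its row is "Hematoma InfraScanner of SDH" (No/Yes) and its column is "Hematoma CT of SDH" (No/Yes). Table 2, the any-hematoma table, carries no type in either label.

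Analysis plan items 6 and 7 ask for counts and test characteristics for each hematoma type, first overall and then within the detection limits. Both are repeated at scan level. Neither item says who forms the comparison group.

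The SAP's definitions are for any hematoma. A positive test is one positive for hematoma, and specificity is the probability of a negative device result "given the patient has no hematoma present".

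On what the device delivers:

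- Protocol section 10 gives the principle that "extravascular blood absorbs NIR light more than intravascular blood".
- The same section says: "Readout of the scan provides information on the severity of a hematoma and identifies the region of the brain bleeding".
- The SAP variable list records "Positive infrascan: Y/N".
- Analysis plan item 4 adds results by quadrant, and item 9 plots "Distributions of Blood Volumes and Difference in Optical Density".

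None of these distinguishes SDH from EDH.

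**The concern.** There are two linked problems. First, the row cannot be filled as labelled, because no variable holds an InfraScanner result for SDH or for EDH.

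Second, the obvious workaround is to use the overall yes/no result, and the column labels then matter. Read as written, No means no SDH on CT. A patient with only an EDH falls there, and if the device correctly detects that EDH the table scores it as a false alarm. No text in items 6 and 7 or in the shell excludes such patients. The specificity and false positive rate from the table would then not be the quantities that the SAP defines.

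At stake is the exploratory objective on the effect of hematoma type (Protocol section 13). With this column, specificity could appear to differ between bleed types only because each table counts a different number of other-type patients as negatives.

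**Working it through.** The documents give no figure for these tables, so there is nothing to reproduce. The check derives the direction and then illustrates the size.

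**Direction.** Let n0 be the patients with no hematoma on CT, o the patients with only another type, Sp the specificity in the n0 patients, and s the detection rate in the o patients. With the overall device result in the row:

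- specificity from the shell = [n0·Sp + o·(1 − s)] / (n0 + o)
- shortfall against Sp = o·[s − (1 − Sp)] / (n0 + o)

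The shortfall is positive whenever s exceeds the false-alarm rate 1 − Sp. It grows with o, so it is largest in the table for the rarer type. This needs no figure for the lesion mix.

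**Inputs for an illustration.**

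- 500 patients (SAP, Study Population) and a hematoma proportion of 0.13 (Protocol section 13, from the interim analysis), assumed to hold for the final sample: 0.13 × 500 = 65 CT-positive and 435 CT-negative.
- Sp = 0.91, the figure both documents cite for the earlier device model. False alarms: 435 × 0.09 = 39.15.
- s from 0.60 to 0.88. The upper value is the earlier model's sensitivity within the detection limits, so it is high for hematomas of any size. The lower value is assumed.
- 5, 10 or 20 EDH and the rest SDH, one type per patient, the same s for both types. All of this is assumed; the documents do not give the mix.

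**Specificity with the No column as labelled.** Example, EDH table with 5 EDH (o = 60) and s = 0.88: 1 − (39.15 + 52.8)/495 = 0.814.

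| EDH / SDH | s | EDH table | SDH table |
|---|---|---|---|
| 5 / 60 | 0.60 | 0.848 | 0.904 |
| 10 / 55 | 0.60 | 0.853 | 0.899 |
| 20 / 45 | 0.60 | 0.862 | 0.888 |
| 5 / 60 | 0.88 | 0.814 | 0.901 |
| 10 / 55 | 0.88 | 0.821 | 0.892 |
| 20 / 45 | 0.88 | 0.836 | 0.875 |

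The shortfall from 0.91 is 0.048 to 0.096 in the EDH table and 0.006 to 0.035 in the SDH table. For scale, the 95% half-width for a specificity of 0.91 in 435 patients is 1.96 × √(0.91 × 0.09/435) = 0.027. With only hematoma-free patients as negatives, specificity is 0.91 in every type table under these inputs.

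**False positive rate.** The SAP defines this as P(B−/A+). From raw counts in the EDH table, with 20 EDH and s = 0.88, it is 78.75/(78.75 + 17.6) = 0.817 with the column as labelled, against 39.15/(39.15 + 17.6) = 0.690 with hematoma-free patients only. With 5 EDH and s = 0.60 it is 75.15/78.15 = 0.962 against 39.15/42.15 = 0.929. The difference runs from 0.03 to 0.13 over these inputs. The high level itself reflects how rare EDH is assumed to be. The SAP intends to report this rate over a range of prevalences, so these values only show the direction.

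**Mixed types.** A patient with both SDH and EDH is in the Yes column of both tables. Each such patient reduces o, so the illustration overstates the shift to the extent that mixed types occur.

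**The case against.** The strongest reply is that the row label is loose wording. Item 6 and the table title promise only results by type, the variable list holds one yes/no result, and an analyst can use nothing else. The shells are visibly drafts. Specificity is already defined on hematoma-free patients, so that definition could be said to settle the comparison group. On this view only a clarification is needed.

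Part of this stands. The SAP does not say in words that other-type patients belong in the No column; that follows from the label and the absence of any exclusion. Items 5 and 7 carry no such label in their text, and for them the matter is only a clarification. But reading the row as the overall result is exactly what makes the column a problem: the shell as labelled and the definition of specificity then give different numbers, and the SAP does not say which prevails.

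The objection to the size also stands. The EDH count, the lower sensitivity and one type per patient are assumptions, and the two accuracy figures belong to an earlier device model. A reader might infer from the table that the EDH shift is sure to exceed the sampling error. It does so throughout this grid, but it would not if s were below about 0.31 to 0.38 (0.09 + 0.0269 × (435 + o)/o, for o = 60 down to 45). The SDH shift exceeds it only with 20 EDH and s above 0.70.

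**Conclusion.** The point holds as an inconsistency between a table shell and the SAP's own definition. The row label has no variable behind it. Filled with the overall device result, the shell understates specificity and overstates the false positive rate in the type tables, provided the device detects the other type more often than it false-alarms. The effect is largest for the rarer type. The direction is firm under that condition; the size cannot be estimated from the documents. The illustrative 0.81 to 0.86 (EDH) and 0.875 to 0.90 (SDH), against 0.91, rest on the assumed mix, detection rates and one type per patient.

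A reader might infer that the study's main accuracy results are affected. They are not: Table 2 has no type label, and its CT-negative column contains only patients without a hematoma. Nor does the denominator affect type-specific sensitivity, which comes from the Yes column. The by-type analysis is exploratory. The correction should still be made before the tables are produced, because it is cheap and removes a spurious difference between types.

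Two nearby gaps are separate clarifications and add no weight here: the entry "Distance-from-cranium: TBD" in the variable list, and CT hematoma type, which Table 1 uses but the variable list omits.

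**What to change.** In the SAP:

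- Relabel the Table 3 row as the overall InfraScanner result, positive or negative.
- Use three CT columns: this type present, only another hematoma type, no hematoma.
- Take sensitivity from the first column and specificity from the third, as the SAP's definition requires. Report the detection rate in the middle column on its own.
- Compute the false positive and false negative rates from the type-specific sensitivity and that specificity over a range of prevalences, as the definitions section already intends.
- State that the same hematoma-free comparison group applies to Analysis plan items 5 to 7. In items 5 and 7, show patients with only out-of-limit hematomas separately.
- Report the number of patients with mixed types, and note that a positive device result in them cannot be attributed to one lesion.

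The cost is SAP wording and one table shell, with no new patients or scans. The type tables would no longer carry a specificity of their own: one value, from the hematoma-free patients, serves them all.
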